Official title: Statin-associated muscle symptoms: in vivo and in vitro studies of mitochondrial function

NCT number: NCT04507373

IRB approved date: 04/25/2018

1. Project Description

1.a Overview. Over 40 million Americans take statins to reduce their risk of atherosclerotic cardiovascular disease (ASCVD). Unfortunately, 10 to 20% stop taking them due to statin-associated muscle symptoms (e.g. pain, aches, weakness, cramps, or stiffness) (1, 2). The pathophysiology of these statin-associated muscle symptoms (SAMS) has remained elusive. Consequently, no objective diagnostic method exists, causing confusion for patient and providers since muscle symptoms can often be multifactorial.

The *overall objectives* of this project are to identify the underlying cause of SAMS and establish an *in-vivo* imaging technique to detect SAMS. **The *central hypothesis* of this proposal is that statins directly inhibit mitochondrial function in SAMS patients.** Our rationale is based on our own preliminary data indicating that simvastatin – the most common statin to cause SAMS – can directly inhibit oxidative phosphorylation (OXPHOS) in mice. Since such changes can be detected *in vivo* in humans utilizing ^{31}P magnetic resonance spectroscopy (MRS) techniques, we will use a state-of-the art 7 Tesla (7T) MRS instrument to study the soleus muscles of SAMS patients. Additionally, we will validate the MRS findings by doing functional studies in muscle biopsy specimens.

We propose double-blind randomized, placebo-controlled pilot study in 15 SAMS patients and 15 controls. Study participants will be treated with simvastatin 40 mg daily or placebo for 10 weeks. We will perform 7T MRS of soleus muscles at randomization and either at first complaint of muscle symptoms or at the end of 10 weeks if no muscle symptoms occur, whichever occurs first. Quadriceps muscle biopsies will also be done immediately following the second MRS scan.

1.b What is the scientific problem that will be addressed and why is this important?

SAMS are prevalent and limit the benefits of lipid lowering. Statins are the second most commonly prescribed medication class in the US (3). Unfortunately, muscle injury – ranging from mild muscle aches to life-threatening rhabdomyolysis – limits their use. Based on observational data, 10-20% of statin users stop treatment within the first year of the initial prescription, citing SAMS as the primary reason (1, 2). Even among adherent statin users, one-third experience interruptions in therapy due to SAMS (4).

The current paradigm for treating SAMS patients is to diagnose subjectively and use trial-and-error approaches to reestablish therapy. These reestablished statin therapy are often at lower doses or with less potent statins, resulting in under-treatment (5-7). Also, since new lipid lowering agents (e.g. PCSK9 inhibitors) are expensive, payers often are unclear as to whether to cover the cost for patients with subjective complaints.

The major gap in knowledge is the effect of statins on muscles. The pathophysiology of SAMS remains unclear. Human genetic studies have implicated genes in hepatocyte drug transport pathways (8), but have failed to provide insight into what is occurring in muscle tissue. Translational studies have raised several possibilities (e.g the roles of Coenzyme Q10, Vitamin D, and circulating cholesterol levels), but results of clinical trials and human genetic studies have failed to support any of these (9-15).

Statins may have an off-target effect: inhibition of mitochondrial function. Our preliminary data indicate that simvastatin lactone (the form that is highly cell permeable)

[figure not shown]

Figure 1: Oxygen consumption rates (OCRs) from mitochondria (0.1mg) isolated from wild type mouse skeletal muscle (tibialis anterior) treated with vehicle or simvastatin (lactone, 100uM) in the presence of complex I substrates (glutamate/malate). Drugs (ADP, oligomycin (oligo), CCCP, antimycin A(antA)) were injected at times indicated.

reduces oxygen consumption rates in isolated mitochondria (Figure 1). Our findings are consistent with prior *in silico* data identifying a binding site for simvastatin in mitochondrial complex III (16).

1.c What are the innovative or high-risk, high-reward approaches that, if successful, might lead to paradigm-shifting results?

We will be able to correlate 7T MRS findings to studies of mitochondrial structure, function, and gene expression. The studies proposed here will allow for an integrated understanding of *in vitro* and *in vivo* changes induced by statins. If our hypothesis is correct, this work will lead to **objective markers** (e.g. MRS signals) that can be used to detect SAMS. Such a tool would shift the current paradigm (i.e. subjective diagnosis) by providing a tool to help providers, patients, and payers determine whether a statin is truly the cause of muscle symptoms. Such a tool could also be used to identify appropriate patients for further studies and follow their therapeutic response.

1.d Does the project address a critical barrier to progress in the field?

Human studies are required since no adequate animal model exists. SAMS has been difficult to induce in preclinical models with statins other than cerivastatin (17-20), perhaps because of lack of muscle exposure when statins are given systemically to animals.

No standardized diagnostic criteria exist for SAMS. The status quo as it pertains to SAMS is to diagnose patients based on their subjective complaints, resulting in confusion for patients, providers, payers, and clinical investigators. Statin withdrawal and rechallenge is often advocated as a diagnostic tool (21), but no evidence-based standardized protocol exists, the sensitivity and specificity remains unknown, and the outcome (self-reported muscle symptoms) remains subjective. A few commercially available diagnostic tests may be used for SAMS patients: blood creatine kinase (CK) levels, solute carrier organic anion transporter family member 1B1 (*SLCO1B1*) rs4149056 genotype, and antibodies to 3-hydroxy-3-methylglutaryl coenzyme A reductase (HMGCR). However, only 5% of SAMS patients develop elevated CK levels, *SLCO1B1* rs4149056 genotype only predicts the risk of extreme elevations in CK in patients on simvastatin (8, 22, 23), and antibodies to HMGCR are responsible only for cases with severe CK elevations (greater than 1000 U/L) that fail to resolve after statins are withdrawn (24). *Thus for 95% of SAMS patients, no diagnostic test helps diagnose SAMS.*

Endpoints and Sample Size. The primary endpoint will be the differences in pre- and post-phosphocreatine relaxation time in SAMS patients on simvastatin compared to placebo. We chose 15 patients/arm since this sample size is within the range of prior pilot and feasibility studies (39).

Patient Recruitment. Table 1 outlines inclusion and exclusion criteria for SAMS patients. We will recruit from existing cohorts (40, 41), and we continue get new SAMS consults in our lipid specialty clinics. We expect to be able to recruit 1 SAMS patients and 1 control per month. Patients will get \$100 per MRS study and \$250 per muscle biopsy.

Table 1. Inclusion and exclusion criteria for SAMS patients

Inclusion Criteria	Exclusion Criteria
Adults, age > 18 yrs or < 80 yrs	Patient who drink large quantities of grapefruit juice (> 1 quart daily).
Patients reporting complaints of statin-associated muscle symptoms, aches, weakness, cramps, or stiffness in the legs.	Patients on the following drugs for which the FDA has issued restrictions for using simvastatin 40 mg daily due to an increased risk of severe muscle injury such as itraconazole, posaconazole, ketoconazole, erythromycin, clarithromycin, telithromycin, HIV-1 protease inhibitors, nefazodone, gemfibrozil, cyclosporine, danazol, amiodarone, amlodipine, ranolazine, and verapamil.
	Patients with muscle-related pain that is not related to statin-use (e.g. muscle aches from strain or trauma) or remains unexplained.
	Any patients with underlying non-statin related muscle disorders.
	Presence of any clinically significant uncontrolled endocrine disease known to influence serum lipids or lipoproteins.
	Conditions of severe acute vascular stress (acute coronary syndrome, ischemic stroke, or major vascular surgery) within prior 3 months.
	Any patients with a history of severe or life-threatening reactions to statins including rhabdomyolysis (defined as evidence of organ damage with CK >10,000 IU/L), CK elevation > 10 times the upper limit of normal, cognitive decline, transaminitis, or allergic reactions.
	History of fibromyalgia or rheumatologic disease with symptoms that may be confounded with statin-related muscle complaints.
	Patients unable to maintain their current activity level or planning to increase their activity level (e.g. new exercise regimen). Such changes may have acute effects on muscle metabolism.
	Pregnant or breast-feeding women. Statins are teratogenic, and the effects of high magnetic fields on a fetus are unknown.
	Women of reproductive age not on effective contraception. Adequate contraceptive measures include intrauterine device (IUD); bilateral tubal ligation; condom or diaphragm plus either contraceptive sponge, foam or jelly.
	Any person with implanted metal, because of MRS safety.
	Use of any active investigational drugs within 1 month or 5 half-lives, whichever is longer.
	History of antibodies to HMGCoA.

MRS Protocol. The MRS protocol has been previously described (35, 36). MR spectra will be measured in the 7T MRI scanner (Achieva, Philips Healthcare, Cleveland, OH).

For in-magnet exercise to elicit depletion of phosphocreatine (PCr) from calf muscle, the subject will be positioned supine and feet-first with the thickest part of the calf positioned in the center of the detection coil and secured by Velcro and a thick cushion pad. The ball of the exercising foot will be in natural contact to the MRI-compatible sand bags which will be fixed on a supporting board attached to MRI bed. The sand bags will provide a resistance to the force exerted by the exercising foot.

The subject will be asked to do exercise after a 2-min baseline 31P MRS scan (TR 4 sec), the exercise will be performed for 90 sec with plantar flexion at a frequency of 4 second by repetitively pushing on and releasing from the sand bags. The pushing duration will be 3 seconds and the releasing 1 second. The subject will be instructed to use maximal force when pushing. After the 90-sec exercise, the subject will be asked to relax but stay still while the scan continues. The post-exercise scan will last for 15 min.

The total scan session, including coil setup, subject preparation/positioning, 31P MRS data acquisition, and subject release from the scanner room, will be ~45 min. If a second bout of exercise is conducted, the scan session will be ~ 1 hr.

Muscle Biopsy Specimens. As described previously (42), muscle tissue will be obtained from the quadriceps muscles, specifically the *Vastus lateralis*, using the percutaneous needle biopsy technique. *The average yield should be 150 +/- 20 mg.* Specimens will be divided as follows: 50 mg will be required to isolate mitochondria and measure oxygen consumption rates (OCRs), 20 mg for electron microscopy studies, and 15 mg for RNAseq studies. The remainder of the sample will be flash frozen at -80°C for potential future studies.

We will isolate mitochondria from fresh muscle biopsy specimens as previously described (42). Muscle homogenates containing equivalent amounts of mitochondria will be distributed into Seahorse analyzer plates, and OCRs will be measured as described (43) using a Seahorse Xfe96 instrument (Seahorse Bioscience, Billerica, MA, USA). Transmission electron microscopy will be done by the UT Southwestern Electron Microscopy Core Facility as described previously (44). Gene expression studies will be done and analyzed by the UT Southwestern McDermott Center core facilities as previously described (45).

Challenges and Potential Problem Areas and Alternative Tactics.

Difficulty with recruiting. If this happens we would expand recruitment to other clinics at UT Southwestern – such as cardiology and primary care - and affiliated private practices.

Mitochondrial function not impaired. We will rely on gene expression data to identify pathways of interest.

P MRS data inconclusive. We would turn to other data that can be obtained from the studies: lactate dynamics and or intramyocellular lipids as measured by ¹H MRS signals.

C3. Timetable – Table 2

2. Significance of Problem to Cardiovascular or Stroke Research

2.a *How will scientific knowledge or clinical practice be impacted if successful?*

Our contribution here is expected to be an **improved understanding** of what changes occur in muscle mitochondria after SAMS patients take statins. Improved mechanistic insight may lead to potential therapeutic interventions targeted at relieving muscle symptoms.

With respect to outcomes, we expect the MRS studies in this proposal will provide **preliminary data** to design a larger randomized, double-blind placebo controlled study of simvastatin in SAMS patients. Such a study will validate this technique as a diagnostic tool for SAMS.

2. b *Will there be an impact on the methods/concepts/technologies?*

We will improve future studies of SAMS patients. Several prior studies of SAMS patients involve statin rechallenges, but these studies have not improved understanding of SAMS (38, 46, 47). One major issue limits their interpretation: none included any objective measure of SAMS, relying instead on self-reported symptoms. The work proposed here will lead to improved clinical trial design. Specifically, this work will lead to objective markers (e.g. MRS signals) that can be used to select appropriate patients and follow their response to therapy.

Table 2. TIMETABLE

AIMS/TASKS	Month 1-6	Month 6-12	Month 12-18	Month 18-24
Patient Recruitment	X	X	X	
MRS Studies	X	X	X	
OCRs	X	X	X	
Electron Microscopy	X	X	X	
Gene Expression				X
Data analysis				X
Manuscript Preparation				X

3. Informatics IIH. The Use of Medicines in the United States: Review of 2012. http://wwwimshealthcom/ims/Global/Content/Insights/IMS%20Institute%20for%20Healthcare%20Informatics/IH_Medicines_in_US_Report_2011pdf. 2012.

**Official title: Statin-associated muscle symptoms: in vivo and in vitro studies of mitochondrial function**

**NCT number: NCT04507373**

**Document date: 7/7/2016**

## Statistical Analysis

The primary endpoint will be the differences in pre- and post-phosphocreatine relaxation time in SAMS patients on simvastatin compared to placebo. We chose 15 patients/arm since this sample size is within the range of prior pilot and feasibility studies. The treatment effect will be estimated by comparing the changes in the patient's pre- and post-phosphocreatine relaxation between the experimental and control arm using the independent t-test. All analyses will be conducted according to the intention-to-treat principle. Significance: A p-value of less than 0.05 will be considered statistically significant. Multiple testing correction will not be applied as this is a pilot study.

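### The primary t-test on change makes no adjustment for the planned baseline scan; ANCOVA would usually be at least as precise, with an expected variance loss of at most about 4% at 15 per arm

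*SAP*

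**What the plan says.** The SAP (Statistical Analysis) defines the endpoint as follows: "The primary endpoint will be the differences in pre- and post-phosphocreatine relaxation time in SAMS patients on simvastatin compared to placebo". The treatment effect is to be estimated by "comparing the changes in the patient's pre- and post-phosphocreatine relaxation between the experimental and control arm using the independent t-test". No baseline covariate, adjusted model or sensitivity analysis is named. The SAP also states "A p-value of less than 0.05 will be considered statistically significant" and "All analyses will be conducted according to the intention-to-treat principle".

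A pre-treatment value of the endpoint is scheduled. Protocol 1.a says "We will perform 7T MRS of soleus muscles at randomization", with a second scan at first muscle symptoms or at 10 weeks.

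On sample size the SAP says "We chose 15 patients/arm since this sample size is within the range of prior pilot and feasibility studies". Protocol 1.a describes the trial as a "double-blind randomized, placebo-controlled pilot study in 15 SAMS patients and 15 controls", which leaves open whether there are 30 SAMS patients or 15. Protocol 1.f (Endpoints and Sample Size) places the comparison within SAMS patients: "relaxation time in SAMS patients on simvastatin compared to placebo".

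**The concern.** A t-test on change already uses the baseline scan, but it fixes the regression slope of post on pre at 1. The slope that minimises variance is r × SD(post)/SD(pre). Where that differs clearly from 1, the change score carries variance that could be removed with data already scheduled. Where it is close to 1, ANCOVA gains nothing and pays a small penalty for estimating the slope.

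Chance baseline imbalance is part of this same variance. It is not a separate bias.

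Precision matters here because the sample size was not set by power. Protocol 2.a says the spectroscopy results are to serve as preliminary data for a larger randomised trial, so the width of the confidence interval largely decides how useful the estimate will be.

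**Working it through.** **Inputs from the documents.** 15 per arm; significance at 0.05 (sidedness not stated, two-sided assumed); one scan at randomisation and one at visit 2.

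**Inputs not in the documents.** The pre-post correlation r, the SDs, the effect size, power and dropout. Ranges are assumed for r and for k = SD(post)/SD(pre).

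**The plan's own figure.** The 15 per arm cannot be reproduced, because no effect size, SD or power is given. For scale, a noncentral-t calculation shows that 15 per arm gives 80% power for a difference of about 1.06 SDs of the change score.

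**Formulas**, n per arm, pre SD set to 1, normal baseline, common slope:

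- Change score: variance = (2/n)(1 + k² − 2rk)
- ANCOVA, expected: variance = (2/n) k²(1 − r²) × (2n − 3)/(2n − 4)
- Ratio = [(1 − r²)k² / (1 + k² − 2rk)] × (2n − 3)/(2n − 4)

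The bracket never exceeds 1 and equals 1 when rk = 1. The second factor is therefore the largest expected loss: 27/26 = 1.038 at n = 15, 13/12 = 1.083 at n = 8, 11/10 = 1.100 at n = 7.

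**Examples at n = 15.**

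- k = 1, r = 0.5: 0.75/1.00 × 1.038 = 0.779
- k = 1.3, r = 0.7: (0.51 × 1.69)/(2.69 − 1.82) × 1.038 = 0.991 × 1.038 = 1.029

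**Expected variance ratio, ANCOVA / change score** (below 1 favours ANCOVA):

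| Setting | r = 0.3 | 0.5 | 0.7 | 0.8 | 0.9 |
|---|---|---|---|---|---|
| 15/arm, equal SDs | 0.675 | 0.779 | 0.883 | 0.935 | 0.987 |
| 15/arm, k = 1.3 both arms | 0.836 | 0.947 | 1.029 | 1.036 | 0.953 |
| 15/arm, k = 1.3 simvastatin arm only (simulated) | 0.77 | 0.88 | 0.99 | 1.03 | 1.04 |
| 8/arm, equal SDs | 0.704 | 0.812 | 0.921 | 0.975 | 1.029 |
| 7/arm, equal SDs | 0.715 | 0.825 | 0.935 | 0.990 | 1.045 |
| 7/arm, k = 1.3 both arms | 0.886 | 1.003 | 1.090 | 1.097 | 1.009 |

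If the post SD is smaller than the pre SD, the gain is larger: at k = 0.8 and 15 per arm the ratio runs from 0.52 to 0.67 for r between 0.3 and 0.9.

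**Break-even with equal SDs.** Here the bracket is (1 + r)/2, so break-even r = 2(2n − 4)/(2n − 3) − 1: 0.93 at 15 per arm, 0.85 at 8, 0.82 at 7.

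**Interval width.** The ratio is the square root of the variance ratio times t(0.975, 27)/t(0.975, 28). At 15 per arm with equal SDs it is 0.82, 0.88, 0.94 and 0.995 at r = 0.3, 0.5, 0.7 and 0.9.

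**Power.** Simulation used 40,000 trials per setting at 15 per arm, with the effect set so that the t-test has 80% power. ANCOVA power was:

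- equal SDs: 93%, 89%, 85%, 81% at r = 0.3, 0.5, 0.7, 0.9
- k = 1.3 in both arms: 87%, 82%, 79%, 79%, 82% at r = 0.3, 0.5, 0.7, 0.8, 0.9

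Both methods rejected a true null in about 5% of trials (0.048 to 0.052).

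**The case against.** The case for leaving the plan alone has four parts.

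1. **Nothing is wrong.** The endpoint is a pre-post difference and the prespecified test compares those differences between arms. The analysis is coherent, valid and unbiased in a declared pilot. This stands, and it limits the point to efficiency.

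2. **The gain cannot be sized from the documents.** They give no r and no SDs, and some settings in the table are losses. This stands as a limit on confidence. It does not reverse the balance: at 15 per arm the expected loss stops at 3.8%, while at r = 0.5 with equal SDs the gain equals having 15/0.779, or about 19, patients per arm. The protocol also makes a very high r hard to presume, because the exercise is self-paced effort against sand bags and the second scan can fall at any time up to 10 weeks. That is inference, not data.

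3. **The 4% is an average over randomisations.** Given the realised baselines, with a true slope of 1, the inflation is 1 + t²/(2n − 2), where t is the baseline-imbalance statistic. At 15 per arm, 5% of trials would have |t| above 2.05, hence inflation above 15%. This is correct, so the 4% must be read as an expected loss. Averaging t² over randomisations gives 28/26, and 1 + (28/26)/28 = 27/26, the same limit as above.

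4. **The sample may be smaller than 15 per arm.** If 15 SAMS patients are split 8 and 7, the limit is 12/11, or 9.1%. With k = 1.3 the ratios at r = 0.5, 0.7, 0.8 and 0.9 are then about 0.99, 1.08, 1.09 and 1.00, so there is no material gain at any of them. This stands, and the two descriptions of the sample need to be reconciled in any case. With equal SDs ANCOVA still gains at that size below r of about 0.83.

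**Conclusion.** The point holds as a recommendation to improve efficiency. The planned t-test is valid.

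At 15 per arm, ANCOVA is expected to be more precise at every r below 0.93 when pre and post SDs are equal. When the post SD is 1.3 times the pre SD, whether in both arms or one, the results are mixed: gains at low r, and losses within the 4% limit where the baseline slope is near 1. Possible gains reach about a third of the variance at r = 0.3 with equal SDs.

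Confidence is medium, because r and the SDs are assumed throughout. The limits also assume a normal baseline, a common slope and complete scans. They rise to about 8% at 8 per arm and 10% at 7 per arm if only 15 SAMS patients are divided between treatments.

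**What to change.** Before unblinding, replace the primary analysis sentence in the SAP. Among randomised SAMS patients, fit an ANCOVA of visit 2 phosphocreatine relaxation time on arm and visit 1 phosphocreatine relaxation time. Report the adjusted difference with its 95% confidence interval and p-value. Keep the change-score t-test as a prespecified sensitivity analysis.

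If a non-SAMS cohort is also randomised, do not pool it into the primary estimate with only a cohort main effect. Either analyse SAMS patients alone, or include an arm-by-cohort interaction and report the SAMS-specific effect.

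The cost is one SAP sentence, no new data and one degree of freedom (more with an interaction). The downside is the expected variance loss given in the verdict, incurred only if the baseline slope is near 1.
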